## MATERIAL AND METHODS

### Study design

This longitudinal, comparative and prospective study conducted between October 2018 and April 2019, is a 2 x 2 randomized controlled trial using a two-group design (BLT vs. control) and two repeated measures (pre- vs. postintervention). In addition, the behavior, mood and physiological parameters of the BLT group participants were assessed immediately before, after and during each session.

This study is performed following the CONSORT (CONsolidated Standards of Reporting Trials) 2010 guideline.

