## Study setting and participants

Participants were recruited between September and October 2018 among residents of the Gerontological Complex La Milagrosa (A Coruña, Spain).

Inclusion criteria: (a) age 65 years or older, (b) diagnosis of dementia, and (c) a score  $\geq 4$  points on the Global Deterioration Scale (GDS; Reisberg et al., 1982), ranging from moderate to very severe cognitive decline.

Exclusion criteria: (a) high ocular sensitivity to light (photosensitivity), (b) preexisting ocular abnormalities, or (c) having any severe ocular disorder that did not allow them to open their eyes or that implied a very low visual acuity.

39 participants will be recruited, stratified according to their cognitive status and subsequently randomly placed into two groups: the BLT group (=19) and the control group (n=20).

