## Measures

Pre- and post-intervention assessments were performed on all subjects in the sample (control and experimental group). Pre-intervention data were collected during the week before the start of the intervention, and post-intervention data were recorded during the week after the end of the intervention. Additionally, data on physiological parameters, mood, and behavior were recorded in each session for the participants of the experimental group.

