### Severe Mini-Mental State Examintation (SMMSE)

Cognitive evaluation: brief assessment of severe cognitive impairment in advanced stages of dementia. This test was applied only to individuals who obtained a score of 10 points or less in the MMSE.

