### **Data management and statistical analysis**

The data of the participants are coded/pseudo-anonymized to ensure confidentiality and users' privacy for research use. Identifiable information is coded with artificial identifiers. The documentation to re-identify the participants will be only available to a medical doctor that collaborates with the research group, ensuring privacy during all data exploitation and dissemination (conferences, Ph.D. thesis, and scientific articles).

The general description of the population studied is performed by univariate analysis. The distribution in the study groups of sociodemographic factors (gender, age, level of education) was evaluated with Student's t test (or Mann-Whitney U test if the assumption of normality is not met or if the sample size is not large enough) for continuous variables and Pearson's Chi-square test for categorical variables. The normal distribution of the variables is tested using the Sapiro-Wilk test. For subsequent analyzes, parametric or non-parametric tests were applied depending on whether the assumption of normality was met or not for each measured variable. Two-way analysis of variance (ANOVA) is used to determine the existence of differences in agitation, behavior, anxiety, cognitive status or severity of dementia at two points in time (pre-vs. post-). Intrasubject variables were considered as intrasubject variables, these measures over time, and intersubject variables were the study group (control or experimental). The differences between the groups are tested by means of the group-tempo interaction. Sphericity assumptions are determined by Mauchly's sphericity test. In case of sphericity transgression, the Pillai trace test or the univariate F-test adjusted to epsilon (Greenhouse-Geisser) (Geisser and Greenhouse, 1958) is performed.

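### The planned group-by-time interaction test is valid, but it fixes the baseline slope at 1 and leaves out the randomisation stratum, so it is usually less precise than ANCOVA for outcomes measured in everyone

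*SAP*

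**What the plan says.** The Study design section describes a randomised trial "using a two-group design (BLT vs. control) and two repeated measures (pre- vs. postintervention". Under Study setting and participants, 39 people are to be "stratified according to their cognitive status and subsequently randomly placed into two groups", with 19 in the light-therapy group and 20 in the control group. The Global Deterioration Scale (GDS) entry range is described as "ranging from moderate to very severe cognitive decline".

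Under Data management and statistical analysis, a two-way ANOVA addresses "differences in agitation, behavior, anxiety, cognitive status or severity of dementia at two points in time". The only between-subject term is named in the words "intersubject variables were the study group (control or experimental", and the comparison is then fixed: "The differences between the groups are tested by means of the group-tempo interaction". No baseline covariate, stratum term or ANCOVA appears anywhere in the SAP. The same section sends variables that fail the normality check to non-parametric tests.

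The Measures section says: "Pre- and post-intervention assessments were performed on all subjects in the sample (control and experimental group". Three cognitive scales are nevertheless restricted. For the SMMSE the SAP says: "This test was applied only to individuals who obtained a score of 10 points or less in the MMSE". CAMCOG is for GDS 4, and SCIP for GDS 5 to 7.

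**The concern.** With two time points, the group-by-time interaction compares mean change between arms. Baseline is used, but its coefficient is set to 1 rather than estimated from the data. If scores before and after are only moderately correlated, a slope of 1 over-corrects and puts baseline noise into the comparison.

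The sample is also stratified by cognitive status before allocation, and the analysis then ignores the stratum. If people at different stages change at different rates, stratified allocation balances that variation between the arms, but the planned model leaves it in the error term. The standard error is then too large and the test is conservative.

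What is at stake is precision in a trial of 39 people. The point concerns five scales that the two-way ANOVA covers and that no section restricts to a subset: CMAI, NPI-Q, RAID, MMSE and BANS-S. It does not concern sleep outcomes, outcomes that go to a non-parametric test, or the three restricted cognitive scales.

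**Working it through.** The SAP states no power, SD or correlation, so there is no figure of its own to reproduce.

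**Inputs from the SAP:** 19 and 20 participants; one pre and one post measure; significance at 0.05.

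**Assumed:** two-sided testing; 80% power; all 39 analysed; pre-post correlation rho; k = post SD divided by pre SD; the number and effect of the strata.

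**1. Equivalence.** A numerical check gave an interaction F of 0.05136 and a squared change-score t of 0.05136, both on 37 df. They are the same test.

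**2. Variances with equal SDs (in units of SD²).** Change score: 2(1 − rho). ANCOVA on baseline: 1 − rho². The ratio is (1 + rho)/2. Estimating the slope costs a factor of 1 + 1/35 = 36/35 and one df (36 instead of 37).

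**3. Detectable difference, by noncentral t.** The standard error factor is √(1/19 + 1/20) = 0.320. At rho 0.5 the change-score SD is √(2 × 0.5) = 1.00. The ANCOVA SD is √0.75 × √(36/35) = 0.878.

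| rho | planned (SD) | ANCOVA on baseline (SD) | power at 0.5 SD, planned / ANCOVA |
|---|---|---|---|
| 0.3 | 1.09 | 0.89 | 25% / 35% |
| 0.5 | 0.92 | 0.81 | 33% / 41% |
| 0.7 | 0.71 | 0.67 | 50% / 56% |
| 0.8 | 0.58 | 0.56 | 67% / 70% |
| 0.9 | 0.412 | 0.408 | 92.5% / 93% |
| 0.95 | 0.291 | 0.292 | no gain |

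Break-even is at rho 0.94. Three further df for an uninformative, balanced stratum raise the ANCOVA figures by 0.001 to 0.004 SD (for example 0.892 to 0.896 at rho 0.3) and move break-even to about 0.93.

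**4. Unequal SDs.** With pre SD 1, the change-score variance is 1 + k² − 2·rho·k and the ANCOVA variance is k²(1 − rho²). Their difference is (1 − rho·k)², which is never negative. Before the 36/35 factor, ANCOVA therefore cannot be worse. Ratios including that factor:
- k = 0.9, rho 0.8: (0.2916/0.37) × 36/35 = 0.81
- k = 1.1, rho 0.8: (0.4356/0.45) × 36/35 = 0.996
- k = 1.2, rho 0.7: (0.7344/0.76) × 36/35 = 0.994

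The baseline gain is larger when the post SD is smaller than the pre SD. It vanishes near rho 0.8 or 0.7 when the post SD is 1.1 or 1.2 times the pre SD. The worst case is rho·k = 1, where the ratio is 36/35 = 1.029, a loss of about 3% of variance.

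**5. Stratum effect, by simulation** (19 against 20, stratified allocation, two or four strata). If the stratum does not predict change, the planned test has size of about 0.05. If it explains 30% of change variance, the size is about 0.02, while ANCOVA with baseline and stratum stays near 0.05. Power at 0.5 SD:

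| rho | planned | ANCOVA, baseline and stratum |
|---|---|---|
| 0.5 | roughly 15–35% | 41–54% |
| 0.9 | about 80–96% | 93–99% |

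The ranges cover both directions of the stratum effect. They also cover two ways of building it: adding stratum variation on top of the other change variance, or holding total change variance fixed. At rho 0.9 the second way gives about 95–96% against 98–99%. Baseline-only ANCOVA can remain conservative (size as low as 0.013), so the stratum term is needed as well.

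**The case against.** The strongest reply is that nothing here is an error. A group-by-time interaction is a conventional pre-post analysis, and preferring a more efficient valid test is close to a matter of taste. That stands as far as validity goes. A reader might infer that leaving out the stratum biases the comparison or inflates false positives. The documents do not support this: under stratified allocation the omission makes the test conservative.

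Second, every size depends on quantities the SAP does not give. This also stands. Nothing shows that rho is low for any of the five scales, and with a modestly larger post SD the baseline gain disappears at ordinary correlations. It would be wrong to say that ANCOVA always wins, or that break-even lies at 0.94 regardless of the SD ratio.

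Third, a large power loss at high rho is partly a matter of how the stratum effect is simulated. This stands too: with total change variance held fixed at rho 0.9, the gap is only a few points.

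Fourth, the scope may shrink, because some of the five scales may go to a non-parametric test. The fix is limited to where the two-way ANOVA would be used.

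What these replies do not remove is the asymmetry. The possible gain is substantial at low or moderate rho or with a predictive stratum, while the loss from the baseline term is capped at about 3% of variance.

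**Conclusion.** The point holds as one of efficiency. The interaction test is valid, but it fixes the baseline slope at 1 and omits a factor used in the allocation. For outcomes measured in all participants it is usually less precise than ANCOVA on baseline and stratum.

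With equal SDs, the baseline term alone lowers the detectable difference by about 0.20 SD at rho 0.3 (1.09 − 0.89), 0.11 at 0.5 (0.92 − 0.81), 0.04 at 0.7 (0.71 − 0.67) and 0.02 at 0.8 (0.58 − 0.56). From 0.9 there is almost no gain. A stratum that predicts change adds to the case for adjustment, clearly at rho 0.5 and less at 0.9. Enrolment spans moderate to very severe decline, so such an effect is plausible, but the SAP gives no figure for it.

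All of this assumes that the 39 are analysed in full. The finding does not extend to small subsets, where ANCOVA can lose: break-even falls to rho 0.87 at an assumed 20 people and 0.73 at 12. The change should be made, but the trial's conclusions are not invalid without it.

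**What to change.** For CMAI, NPI-Q, RAID, MMSE and BANS-S, wherever the SAP would use the two-way ANOVA, test the group difference by ANCOVA of the post score on group, the participant's own baseline score and the cognitive-status stratum as used at randomisation. Report the adjusted mean difference with its 95% confidence interval. Keep the planned interaction test for CAMCOG, SCIP and SMMSE.

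The study ran from October 2018 to April 2019 and the SAP names 2020 software, so outcomes may already have been seen. If so, label the ANCOVA post hoc and report it beside the planned interaction test for every one of these outcomes, so that neither result is chosen after the fact.

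The cost is small. No new data are needed, and the named software fits the model. The baseline uses one df and the strata a few (three if the strata were the four GDS levels 4 to 7, which is an assumption). Where the baseline does not help, its term costs at most about 3% of variance.

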## OBJECTIVES

To study the short- and long-term effects of bright light therapy on mood, behavior, sleep and cognition in a sample of institutionalized older adults with moderate to very severe dementia.

To explore the immediate effects of bright light therapy sessions on behavior, mood and physiological parameter in a sample of institutionalized older adults with moderate to very severe dementia.

To compare the effectiveness of bright light therapy sessions with other non-pharmacological interventions in people with dementia.

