The Wilcoxon signed-rank test or the Paired t test are employed to measure significant changes between the Interact short scores from before to after the intervention sessions for each of the assessed mood and behavior items. Likewise, these same tests are used to analyze the evolution of the Interact during scores, comparing the average scores of the first week with those of the fourth week. In addition, the evolution of mood and behavior scores throughout the four weeks of treatment is analyzed with the Friedman test for related samples. The Paired t test is also used to determine the existence of any differences from before to after the sessions in physiological parameters. In the variables in which statistically significant differences are found, Cohen's  $d$  or  $r$  values are used to report the effect size (ES) of these changes. The interpretation of the importance of the ES is made according to the benchmarks defined by Cohen, as follows: small ES ( $d = 0.2$  or  $r = 0.1$ ), medium ES ( $d = 0.5$  or  $r = 0.3$ ), and large ES ( $d = 0.8$  or  $r = 0.5$ ).

The significance threshold is set at a p-value of less than 0.05. All data analysis are performed with the statistical programs SPSS (version 25.0), RStudio software package (Version 1.3.1093) and JAMOVI (The jamovi project, 2020, Version 1.2).

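### Effect sizes are reported only for significant results, and the randomised group-by-time comparison is planned as a test with no estimate or confidence interval

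*SAP*

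**What the plan says.** All the relevant text is in the SAP section Data management and statistical analysis.

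- **Randomised comparison.** The two-way ANOVA "is used to determine the existence of differences in agitation, behavior, anxiety, cognitive status or severity of dementia" before and after the intervention. Then: "The differences between the groups are tested by means of the group-tempo interaction". Sphericity checks follow. The section names no between-group difference, confidence interval or effect size for this interaction.
- **Within-BLT tests.** The next paragraph sets out paired t, Wilcoxon and Friedman tests on the Interact scales and paired t tests on the oximeter readings. The sections Interact scale and Pulse oximeter confine both measures to the experimental group.
- **Effect sizes.** Straight after those tests comes the rule. Its condition is "In the variables in which statistically significant differences are found". Only where that condition is met does the SAP call for a standardised measure, d or r, to describe the changes just tested. Cohen's benchmarks then grade importance, with small at d = 0.2 or r = 0.1, medium at 0.5 or 0.3, and large at 0.8 or 0.5.
- **Threshold.** A p-value below 0.05. Sidedness is not stated.

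The first item under Objectives is "To study the short- and long-term effects of bright light therapy on mood, behavior, sleep and cognition". Exploring immediate effects is a separate, second objective.

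**The concern.** The SAP states a reporting rule here; it does not merely leave a gap. Following it has two consequences.

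First, an effect size appears only after its variable has passed a significance filter. In a small sample the results that pass are disproportionately those where chance enlarged the effect, so the displayed values are too large on average. The benchmarks are then applied to these selected values.

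Second, the comparison that randomisation protects receives no planned magnitude. If its interaction test is not significant, the plan provides neither an estimate nor an interval, and a reader cannot see which effects remain compatible with the data. This matters most at the sizes here: at most 19 vs 20, and fewer for SMMSE, CAMCOG and SCIP, which the SAP gives only to subsets of participants.

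**Working it through.** The SAP contains no power or effect-size calculation to reproduce. The figures below show what the reporting rule does.

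**Inputs from the SAP:** 19 BLT and 20 control participants (Study setting and participants); 20 scheduled sessions, with at least 16 needed to count as a completer (Intervention); threshold 0.05.
**Assumed:** two-sided tests, normal data, and the true effects used.

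**1. Smallest significant paired effect (participant as unit, d scaled by the SD of change)**
t(0.975, 18)/√19 = 2.101/4.359 = 0.48.

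**2. Effect of the filter (simulation, n = 19)**

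| True d | Power | Mean \|d\|, significant only | Mean \|d\|, all results |
|---|---|---|---|
| 0.2 | 13% | 0.62 | 0.26 |
| 0.5 | 54% | 0.71 | 0.52 |
| 0.8 | 91% | 0.88 | 0.84 |

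Both columns of means are absolute, so they compare like with like. In signed terms, at true d = 0.2, the means are 0.60 (significant only) and 0.21 (all). In absolute terms the filter multiplies the mean by 0.62/0.26 = 2.4 at true d = 0.2, by 0.71/0.52 = 1.4 at 0.5, and by 0.88/0.84 = 1.05 at 0.8.

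**3. Sensitivity to choices the SAP does not state**
- *SD used for d.* If d is scaled by the raw-score SD, the minimum becomes 0.482 × √(2(1 − ρ)), with ρ the pre-post correlation. For assumed ρ of 0.7, 0.8 and 0.9 this gives 0.37, 0.30 and 0.22.
- *Unit.* If sessions are treated as independent pairs, there are 19 × 16 = 304 to 19 × 20 = 380 of them. The smallest significant d is then 0.11 to 0.10. At true d = 0.2 the mean among significant results is 0.20 to 0.21, so there is almost no inflation. At true d = 0.1 it is 0.14 to 0.15. This alternative is not open for the during-session Interact analysis described as "comparing the average scores of the first week with those of the fourth week", because averaging by week makes the participant the unit.

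**4. The randomised comparison (19 vs 20)**
With two groups and two time points, the interaction test is equivalent to a two-sample t test on change scores.
- Smallest significant |d|: t(0.975, 37) × √(1/19 + 1/20) = 2.026 × 0.3204 = 0.65.
- 95% CI half-width: 1.96 × √(39/380 + d²/78), which is 0.63 at d = 0.2 and 0.64 at d = 0.6.
- An observed 0.2 is therefore compatible with −0.43 to 0.83, and a non-significant 0.6 with about −0.04 to 1.24.

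**The case against.** **The sentence may cover the ANOVA outcomes too.** It speaks of variables in general, stands near the end of the section, and the preceding paragraph also speaks of differences. A reader might infer from its position that effect sizes are definitely restricted to within-BLT changes. Position, the phrase about these changes, and the choice of d and r (which suit paired t and Wilcoxon tests) favour that reading but do not settle it. The broader reading cures nothing, however: the pre/post outcomes would face the same filter, and there would still be no CI.

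**The inflation depends on unstated choices.** This stands. A reader might infer that small effects could hardly ever be reported. That holds with the participant as unit and d scaled by the SD of change. It fails if sessions are the unit, and it weakens if d is scaled by a raw-score SD with high pre-post correlation.

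**The imprecision comes from sample size, and a CI would not cure it.** Also true. To exclude d = 0.5, the observed d would have to be about −0.13 or lower (−0.13 + 0.63 = 0.50). With no true effect that happens in about 34% of trials. An interval shows the imprecision; it usually would not rule out a medium effect.

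**A reader can recover d, and a guideline is cited.** With two groups and two times, d = √(F × (1/19 + 1/20)). This needs F and the group sizes to be published for every outcome, to which the SAP does not commit, and it fails where the non-parametric route replaces the ANOVA. The Study design section says "This study is performed following the CONSORT" 2010 guideline. That general statement does not override a specific rule that conditions on significance.

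**The within-BLT tests serve their own objective.** Correct. Measuring immediate effects in one arm is by design and is not criticised here.

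**Conclusion.** The point holds. Effect sizes are conditional on p < 0.05, and no estimate or CI is planned for the randomised comparison; both follow from the text whichever way the effect-size sentence is read. Under the participant-level assumptions the filter raises the mean |d| from 0.26 to 0.62 at a true d of 0.2, from 0.52 to 0.71 at 0.5, and from 0.84 to 0.88 at 0.8. These figures rest on assumed true effects, two-sided testing and the SD of change, and the bias is slight with session-level units from d = 0.2 upward. Between groups, anything below |d| = 0.65 goes unreported as a magnitude, although the interval around it is about ±0.63.

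A reader might go further and infer that the planned tests or their error rates are wrong, or that adding intervals would make null results conclusive. Neither follows: this is a defect of reporting. It should be corrected. The unit of analysis for the pre/post-session Interact and oximeter tests is a separate question, and this finding does not depend on it.

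**What to change.** In Data management and statistical analysis, replace the condition that limits effect sizes to significant variables with:

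*For every analysed variable, whatever its p-value, the estimate, its 95% CI and the effect size are reported, including the between-group difference in pre-post change for each pre/post outcome, with the number analysed per group.*

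Add one sentence naming the SD used for d.

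The change needs no new data and no further tests. It costs a longer results table and more cautious conclusions, because many intervals will be wide at 19 vs 20 or fewer.

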### Intervention

BLT sessions were carried out in a quiet room of the Gerontological Complex especially enabled for their proper development and were implemented by a research psychologist specialized in Gerontology. The devices used for the intervention were bright white light lamps providing an intensity of 10,000 lux. Four users participated in each session, placing two users per lamp, seated in a comfortable chair with armrests 70 cm from the lamp. The sessions were 30 minutes/day in the time slot between 10:30 and 12:00 in the morning, 5 days a week (Monday to Friday) for 4 weeks (total 20 sessions). Two groups of participants per day were established, the first shift being from 10:30 to 11:00, and the second from 11:15 to 11:45 a.m., which means the stimulation of 8 people per day (month). During the sessions, while exposed to light, participants were watching documentaries on neutral topics (nature, Spanish and Galician culture, etc.). Each session lasted 30 minutes, unless the participant expressed the desire to

leave the room and could not be convinced to remain in it without generating agitation. Participants who responded negatively to light exposure were immediately withdrawn from the intervention. Only those sessions in which the person remained at least 80% of the expected time ( $\geq 22.5$  minutes) were considered as sessions performed. Additionally it is established as a final criterion to consider the participant to complete at least 80% of the scheduled sessions (16 out of 20 sessions).

In every session, the researchers supervised the users to ensure full compliance with the treatment and recorded the physiological parameters (heart rate and blood oxygen saturation) as well as the mood and behavior of the participants.

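### Effect-size labels for the Interact changes depend on whether d or r is used: the two sets of cut-offs do not match for paired data, and neither measure is defined

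*SAP*

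**What the plan says.** All of this is in the SAP, section Data management and statistical analysis, unless another section is named.

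- **Choice of test.** The general rule is that "parametric or non-parametric tests were applied depending on whether the assumption of normality was met or not for each measured variable". For the session data, "The Wilcoxon signed-rank test or the Paired t test are employed to measure significant changes between the Interact short scores", item by item. The same pair of tests is applied to the scores taken during sessions, "comparing the average scores of the first week with those of the fourth week".
- **Effect size.** Where a variable is significant, d or r "values are used to report the effect size (ES) of these changes". No formula is given for either.
- **Labels.** "The interpretation of the importance of the ES is made according to the benchmarks defined by Cohen", with one set for d (0.2, 0.5, 0.8) and another for r (0.1, 0.3, 0.5).
- **Threshold.** "The significance threshold is set at a p-value of less than 0.05".
- **Size of the analysis.** Study setting and participants gives "the BLT group (=19) and the control group (n=20"; only the light-therapy group has session data. Intervention schedules "5 days a week (Monday to Friday) for 4 weeks (total 20 sessions".

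**The concern.** The SAP uses these labels to say how important the immediate effects are. That is its second objective, and it is studied in one arm without a control. The SAP does not state which measure goes with which test, but the natural reading is d with paired t and r with Wilcoxon. A normality check on at most 19 people then decides, item by item, which set of cut-offs applies.

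If the sets do not agree, two Interact items with the same underlying change can be given different importance only because one failed the normality check. Two undefined quantities add to this: the SD that divides the change in d, and whether N in r = Z/√N counts pairs or observations. Both can be chosen after the results are seen.

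**Working it through.** The SAP gives no computed figure on this point, so there is nothing to reproduce.

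**Inputs from the SAP:** 19 people in the light-therapy group, p < 0.05 (taken as two-sided), the two sets of cut-offs, and at most 5 sessions per week. **Assumptions:** one pair per person, normal data for the simulation, and values for correlation and intraclass correlation (ICC), none of which the SAP gives.

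**1. Do the cut-offs match?** For two independent groups, r = d/√(d² + 4). For 19 pairs with d on the SD of the differences, t = d√19 and r = t/√(t² + 18).

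| d | r, independent groups | r, 19 pairs | SAP cut-off for r |
|---|---|---|---|
| 0.2 | 0.100 | 0.20 | 0.1 |
| 0.5 | 0.243 | 0.46 | 0.3 |
| 0.8 | 0.371 | 0.64 | 0.5 |

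On the paired scale, r = 0.5 means t² = 0.25(t² + 18), so t² = 6 and d = √6/√19 = 0.56. A paired d between 0.56 and 0.80 is thus *medium* by d and *large* by this r. Wilcoxon r = Z/√pairs behaves much like it. Counting observations divides that r by √2 and mostly moves the label the other way.

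**2. How often do the labels differ?** Normal samples of 19 differences were simulated, keeping those significant by both tests, because only significant variables receive a label.

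| True d | Labels differ, r = Z/√pairs | Labels differ, r = Z/√observations |
|---|---|---|
| 0.5 | about 56% | about 17% |
| 0.6 | about 51% | 17% to 18% |
| 0.8 | about 35% | about 19% |
| 1.0 | about 17% | about 17% |

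At a true d of 0.6, *large* is assigned in 36% by d, 85% to 86% by r on pairs and 21% by r on observations. With pairs, every disagreement puts r in the higher class.

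**3. Effect of labelling only significant results.** The smallest significant values with 19 pairs are:
- d = 2.101/√19 = 0.48
- r = 1.96/√19 = 0.45 (pairs)
- r = 1.96/√38 = 0.32 (observations)

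Both r values are above the 0.3 cut-off, and the d value is just below 0.5. At a true d of 0.6, about 4% of results significant by the t test have d below 0.5.

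**4. Dependence on the standardiser.** On the SD of the differences, d = (change/SD of scores)/√(2(1 − ρ)). A change of 0.4 SD gives:
- 0.34 at ρ = 0.3 (*small*)
- 0.63 at ρ = 0.8 (*medium*)
- 0.89 at ρ = 0.9 (*large*)

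On the raw-score SD it is 0.40 at every ρ.

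**5. Dependence on averaging.** The only averaging stated is week 1 against week 4, at most 5 sessions each. Take a change of 0.3 single-session SD, ICC 0.5 and a between-person variance of the change of 0.1:
- SD of the differences, one session: 0.3/√(0.1 + 1) = 0.29
- SD of the differences, five sessions: 0.3/√(0.1 + 1/5) = 0.55
- Raw-score SD: 0.30 for one session and 0.3/√(0.5 + 0.5/5) = 0.39 for five

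The change is the same throughout. On the SD of the differences the label moves from *small* to *medium*; on the raw-score SD it stays *small*.

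**The case against.** The SAP gives separate, conventional cut-offs for d and r and states them openly. It does not mix up the two scales, and within either scale the label still rises with the change: at ρ = 0.5, changes of 0.2, 0.3, 0.4 and 0.5 SD give d of 0.20, 0.30, 0.40 and 0.50. A reader might infer that the label has nothing to do with the size of the change. The documents do not support that; the label depends on other things *as well*.

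Three further readings go too far:

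- **That *small* can never be reported.** The minimum significant d of 0.48 is itself below 0.5. With a raw-score SD the minimum is 0.48 × √(2(1 − ρ)), which is 0.22 at ρ = 0.9. If the unit were the session (up to 19 × 20 = 380 pairs), significance would start near d = 0.10.
- **That d is necessarily on the SD of the differences.** The SAP says only Cohen's d. With a raw-score SD the dependence on correlation disappears and the averaging effect is modest.
- **That before/after scores are averaged over 20 sessions.** The SAP does not say so.

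It is also fair that the simulation scores r on normal data, where the plan would choose t. It shows that the scales disagree on the same data, not how often the plan would mislabel an item. The physiological parameters use only the paired t test, so the switch between d and r does not reach them.

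These points limit the claim. They do not make the two sets of cut-offs equivalent for paired data, and they do not supply the missing definitions.

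**Conclusion.** The concern holds in a limited form. A stated rule lets a normality check choose between two importance scales that disagree for paired data, and it leaves d and r undefined. The percentages rest on 19 person-level pairs, d on the SD of the differences, normal data and the true d shown. The gap between about 51% and 17% to 18% at a true d of 0.6 comes only from the N in r, which the SAP does not specify. The dependence on correlation and averaging applies if d uses the SD of the differences, and its size rests on assumed values.

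What is at stake is the description of importance in the uncontrolled Interact analyses. No p-value and no between-group comparison changes. This is an inexpensive improvement, not a fault that undermines the trial's main comparison.

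**What to change.** In Data management and statistical analysis, replace the effect-size sentences as follows:

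1. Report every before/after and week-1/week-4 change in natural units with a 95% CI, whether or not it is significant.
2. If a standardised value is kept, use one definition for all Interact items, whichever test gives the p-value. State the standardiser and the unit of analysis, including how many sessions are averaged.
3. Do not base statements of importance on labels drawn from a mixture of d and r.

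The cost is a few sentences of SAP text and a few lines of analysis. The downside is that some effects that would now be called *large* will look smaller. A standardised value will still move somewhat with the number of sessions averaged, so the unit must be stated and the natural-unit result should come first.
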